#### 7.1.4.8 *Outpatient Assessments*

- 7-point ordinal scale of clinical status (Daily scores through Day 28 will be evaluated and will be based on weekly assessments performed on Day 8, Day 15, Day 22, and Day 28 [ $\pm 2$  days].)
- Documentation of pacritinib/placebo dosing for patients who continue treatment after discharge from the hospital
- AEs (will be documented through 30 days after the last dose of pacritinib/placebo and will be based on weekly assessments [ $\pm 2$  days] through 30 days after last dose)

- Concomitant medications (will be documented through 30 days after the last dose of pacritinib/placebo and will be based on weekly assessments [ $\pm 2$  days] through 30 days after last dose)

Note: Outpatient assessments should be based on weekly telephone/videoconference communication with the patient and include an evaluation of the **daily** 7-point ordinal scale score for the days between contacts and daily pacritinib/placebo dosing as outlined in [Table 1](#). More frequent telephone/videoconference contact may occur as needed to supplement the above assessments. Review of medical records may also be performed as needed to supplement these assessments; medical records should be reviewed for patients who cannot be reached by telephone/videoconference.

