## 6.2 Secondary Efficacy Endpoints

### 6.2.1 Number of Ventilator-Free Days

The number of total ventilator-free days is defined as the number of total days that patients are alive and not intubated, from Day 1 to Day 28. The number of total ventilator-free days will be calculated as:

- Number of ventilator free days = Number of total days with clinical status assessment of 5 or less from Day 1 until Day 28

Ventilator-free days includes all episodes a patient is not on IMV and/or ECMO and report a clinical status form of 5 or less from Day 1 to Day 28.

Patients who discontinued early will be considered as being ventilator-free up to Day 28 if they were discharged from the clinical facility (discharge date is not missing), in which case they will be considered as not having an event of IMV and/or ECMO up to Day 28. Patients who discontinued early and were not discharged from the clinical facility will be considered as being ventilator-free up to the time of study discontinuation.

### 6.2.2 Mortality Rate at Days 15 and 28

The 15-day mortality rate is defined as the proportion of patients with outcome of death during the 15 days following randomization. The Day 15 mortality rate is calculated as:

- $(\text{Number of patients that die by Day 15}) / (\text{Number of patients in the ITT population})$

The 28-day mortality rate is defined as the proportion of patients with outcome of death during the 28 days following randomization. The Day 28 mortality rate is calculated as:

- $(\text{Number of patients that die by Day 28}) / (\text{Number of patients in the ITT population})$

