### **7.1.4 Handling of Dropouts or Missing Data**

Unrecorded data values will be recorded as missing. Only recorded (i.e. complete) data values will be used for statistical analyses. In general, invalid or missing values will not be imputed in the data unless stated otherwise.

In addition, analysis methods for handling dropouts are specified under the endpoint definition.

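### Ventilator-free days are counted from recorded forms, so an unrecorded day in a patient still on study scores like a ventilated day, while a discharged patient who leaves is credited to Day 28

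*SAP*

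**What the plan says.** Protocol 11.1.1 defines this secondary endpoint by whether the patient is alive and free of intubation from randomization to Day 28, with no reference to a form. SAP 6.2.1 opens with the same idea and then gives the calculation: "Number of total days with clinical status assessment of 5 or less from Day 1 until Day 28". It adds a counting condition: "Ventilator-free days includes all episodes a patient is not on IMV and/or ECMO and report a clinical status form of 5 or less".

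SAP 6.2.1 has two rules for incomplete follow-up, both for early discontinuers:
- Discharged: "Patients who discontinued early will be considered as being ventilator-free up to Day 28 if they were discharged from the clinical facility", and "they will be considered as not having an event of IMV and/or ECMO up to Day 28".
- Not discharged: those who "were not discharged from the clinical facility will be considered as being ventilator-free up to the time of study discontinuation".

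The general rule in SAP 7.1.4 is "Only recorded (i.e. complete) data values will be used for statistical analyses". The same section leaves gaps unfilled as a rule, except where the SAP provides for them elsewhere.

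Protocol 7.1.1.1 asks for a daily score through Day 28, including after discharge. Under Protocol 7.1.4.8 the outpatient scores "will be based on weekly assessments performed on Day 8, Day 15, Day 22, and Day 28", each with a window of 2 days either side. Each contact is meant to cover the days since the previous one, and records are to be reviewed when a patient cannot be reached.

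SAP 7.4.2.1 compares the arms with a Wilcoxon rank sum test.

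**The concern.** The definition and the calculation differ whenever a form is absent. By the definition, a day at home without a form is ventilator-free. By the calculation it adds nothing, as does a day intubated or dead. No rule covers such a day in a patient who remains on study.

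A patient who leaves the study after discharge does have a rule, and it is generous: full credit to Day 28. Two patients with the same clinical course can therefore score differently, and the one who stays in follow-up can score lower.

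The discharge rule is also loosely worded. The matching rule in SAP 6.1 is limited to patients who had not progressed; the one in 6.2.1 has no such limit.

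At stake is what the first-listed secondary endpoint measures. Part of it becomes completeness of outpatient forms. If completeness differed between arms, the comparison would carry that difference.

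**Working it through.** **1. Planning figures.** The documents give no numerical assumption for ventilator-free days. The event rates used below come from the sample-size statement (SAP 3.4): 13.5% and 26.5%, one-sided 0.10, 80% power, about 200 patients.
- Uncorrected n per arm = [1.2816 × √(2 × 0.20 × 0.80) + 0.8416 × √(0.135 × 0.865 + 0.265 × 0.735)]² / 0.13² = 84.5, so 85.
- With continuity correction: (84.5 / 4) × [1 + √(1 + 4 / (84.5 × 0.13))]² = 99.3, so 100 per arm and 200 in total. The plan's figure is reproduced.

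At these rates 100 − 26.5 = 73.5% to 100 − 13.5 = 86.5% of patients have no IMV, ECMO or death. By the definition all of them should tie at 28.

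**2. The counting rule applied to example patients.** SAP score = number of days from 1 to 28 with a recorded score of 5 or less, plus any early-discontinuation credit.

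| Patient | SAP score | Days alive and not ventilated |
|---|---|---|
| Never ventilated, discharged Day 10, all forms present | 28 | 28 |
| Same, on study, Days 16–22 unrecovered | 28 − 7 = 21 | 28 |
| Same, on study, last contact on Day 26 | 28 − 2 = 26 | 28 |
| Same, on study, no forms after Day 10 | 10 | 28 |
| Same, left the study on Day 10 after discharge | 10 + 18 = 28 | 28 if never ventilated later |
| Never ventilated, left on Day 10 without discharge | 10 | not known after Day 10 |
| Ventilated Days 5–11, all forms present | 28 − 7 = 21 | 21 |

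The second row equals the last: 7 unrecovered days cost as much as 7 days on a ventilator. The third row needs no protocol deviation, because Day 26 lies within the window of the Day 28 contact. Table 1 of the protocol lists no clinical status score at the 30-day follow-up.

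**3. The discharge rule read literally.** Take a patient ventilated on Days 3–12 (10 days), discharged on Day 20, who then leaves the study. Days alive and not ventilated: 28 − 10 = 18. If the rule is programmed as no IMV/ECMO event up to Day 28, the score is 28.

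**4. Sensitivity of the Wilcoxon test.** The documents give no rate of unrecovered forms, so this is an illustration. Assumptions: 100 per arm; one-sided 0.10 (the SAP states no level for this endpoint); patients with an event score uniformly from 0 to 21; all others are discharged by Day 10; the three later contacts cover Days 11–15, 16–22 and 23–28; each is lost independently and never recovered; 3,000 runs.

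| True event rates, pacritinib / placebo | Contacts lost, pacritinib / placebo | Rejection rate |
|---|---|---|
| 13.5% / 26.5% | 0 / 0 | 84% |
| 13.5% / 26.5% | 5% / 5% | 73% |
| 13.5% / 26.5% | 10% / 10% | 68% |
| 13.5% / 26.5% | 20% / 20% | 61% |
| 20% / 20% | 0 / 0 | 10% |
| 20% / 20% | 20% / 20% | 9% |
| 20% / 20% | 5% / 15% | 83% |
| 20% / 20% | 15% / 5% | 0% |

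The mean differences can be checked by hand. With full forms at the planning rates: 0.13 × (28 − 10.5) = 2.3 days. With no true effect and 5% against 15% lost: 0.80 × 0.10 × 18 outpatient days = 1.4 days. The simulation gave 2.28 and 1.43. Equal loss lowers power but leaves the error rate at about 10%; only unequal loss shifts the comparison.

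**The case against.** A reader might infer that every missed weekly call removes 7 days. The documents do not support that. Under Protocol 7.1.4.8 and note 3 to Table 1, the next contact can cover the days since the last one, extra contacts are allowed, and records are reviewed for patients who cannot be reached. A day is lost only if all of these fail, or if it falls after the last contact and nobody goes back for it. The simulation allows no recovery and so shows sensitivity, not an expected effect.

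A reader might also infer that SAP 7.1.4 forbids imputation outright. It does not: it speaks in general terms, allows stated exceptions, and refers dropouts to the endpoint definitions. Nor does the SAP say that a missing form counts as ventilated. That follows from the formula, the condition that a form be reported, and the recorded-values rule. The opening definition in 6.2.1 points the other way, so the section disagrees with itself.

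A third tempting reading is that the plan erases observed intubations. More probably the discharge rule is meant to fill the days after a patient leaves, since deleting recorded scores of 6 would contradict the definition above it. What stands is that 6.2.1 omits the condition that 6.1 contains, so the text does not exclude that programming.

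Finally, the trial is double-blind and nothing in the documents suggests that form completion will differ by arm. The endpoint is secondary, and Protocol 11.3 plans only descriptive statistics for it. These points limit the weight of the concern. They do not supply the missing rule.

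**Conclusion.** The point holds as a defect in the calculation rule. Unrecorded days in patients still on study score 0, while discharged patients who leave are credited to Day 28, so leaving can score better than staying. The individual effect ranges from 2 days (last contact on Day 26) to 7 days for one unrecovered weekly interval, and more if several are lost. Because 73.5% to 86.5% of patients should tie at 28, even small losses change ranks.

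The documents do not support a claim that the comparison will be biased, or by how much. That depends on the share of unrecovered forms and on whether it differs by arm, and neither is given. The discharge-rule problem is one of ambiguous wording, with an 18-against-28 example if it is programmed literally. The primary analysis and the sample size are unaffected. The correction is worth making before unblinding.

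**What to change.** Rewrite the calculation in SAP 6.2.1:
- **Patients on study, and discharged patients:** ventilator-free days = 28 minus the number of days from Day 1 to Day 28 at status 6 or 7. An unrecorded day takes the last recorded status, and death is carried to Day 28.
- **Discharged patients who leave the study:** discharge credit applies only to days after the last recorded assessment. Every observed day at 6 or 7 remains counted.
- **Patients who leave without discharge:** keep the present rule of no credit after study discontinuation, and state that observed days at 6 before that date are not credited.

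The third rule is needed because unrestricted carry-forward would credit an inpatient at score 5 who withdraws on Day 4 with 28 days, although SAP 6.1 counts that patient as progression.

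Under these rules the on-study patients in the first four rows of the example table all score 28. The patient ventilated on Days 5–11 stays at 21, the one ventilated on Days 3–12 scores 18, and the one who left undischarged on Day 10 stays at 10.

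The cost is SAP wording and simple programming, with no new data. The downside is that status is carried forward over what should be a small number of unrecorded days. Reporting that number by arm would show whether it matters.

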## **Secondary Endpoints**

1. The number of ventilator-free days, defined as the number of days that patients are alive and not intubated, from randomization to Day 28
2. The mortality rate at Day 28 is defined as the number of patients with outcome of death during the 28 days following randomization divided by the total number of patients in the ITT population
3. The mortality rate at Day 15 is defined as the number of patients with outcome of death in the 15 days following randomization divided by the total number of patients in the ITT population.
4. The time to improvement by at least 2 points relative to Baseline on the 7-point ordinal scale of clinical status. All enrolled patients will have a score between 3 and 5 by virtue of being hospitalized and non-intubated; therefore, patients who progress from 3 to 1, from 4 to 2, or from 5 to 3 will have met the definition of improvement.
5. The clinical status as assessed by the 7-point ordinal scale of clinical status at Days 8, 15, 22, and 28.
6. The rate of use of immunomodulatory agents as treatment for COVID-19 is defined as the proportion of patients reporting use of medications such as corticosteroids, tocilizumab, anakinra, or eculizumab as treatment for COVID-19, during 28 days following randomization divided by the patients in the ITT population.

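### SAP 6.2.1 counts a day with no clinical status form as not ventilator-free in patients who stay in the study, so a never-ventilated completer can score below a discharged patient who withdrew

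*SAP*

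**What the plan says.** The protocol (11.1.1, Secondary Endpoints) gives the endpoint as ventilator-free days, "defined as the number of days that patients are alive and not intubated, from randomization to Day 28". SAP 6.2.1 opens with nearly the same concept, "the number of total days that patients are alive and not intubated, from Day 1 to Day 28", but the formula that follows is "Number of total days with clinical status assessment of 5 or less from Day 1 until Day 28". The next sentence confirms that a form is needed: the patient must not be on IMV or ECMO and must "report a clinical status form of 5 or less from Day 1 to Day 28".

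On missing data, SAP 7.1.4 states "Only recorded (i.e. complete) data values will be used for statistical analyses" and adds "In general, invalid or missing values will not be imputed in the data unless stated otherwise". It leaves dropouts to the endpoint definitions. In 6.2.1 that handling covers early leavers only: "Patients who discontinued early will be considered as being ventilator-free up to Day 28 if they were discharged from the clinical facility"; those not discharged are credited up to the day they discontinue. Nothing covers a blank day in a patient who does not discontinue.

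After discharge, Protocol 7.1.4.8 says that daily scores "will be based on weekly assessments performed on Day 8, Day 15, Day 22, and Day 28", each with a window of 2 days either side. The note to that section and footnote 3 of Table 1 have each contact cover the days since the previous one. SAP 7.4.2.1 compares the arms with a Wilcoxon rank-sum test.

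**The concern.** The formula and the definition agree only if every day from 1 to 28 carries a form. Where a form is absent and the patient is still in the study, the day adds nothing, exactly as a day on a ventilator would. The patient may have been at home and breathing unaided.

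This produces an inverted ordering. A discharged patient who leaves the study is credited to Day 28 by rule, while one who stays is credited only for days with a form. Less follow-up can earn the better score.

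A loss of 1 or 2 days would be trivial for a mean, but not for a rank test on an outcome where most patients share the maximum. Any value below 28 falls beneath the whole tied block, so a scheduling artefact competes with real ventilation in the ranking.

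**Working it through.** **Plan's own figures.** The plan gives no power or precision figure for ventilator-free days. Its one sample-size figure is for the primary endpoint (SAP 3.4): about 200 patients, 80% power, 13.5% versus 26.5%, one-sided 0.10. The continuity-corrected two-proportion formula reproduces it at 100 per arm. It is used here only as the source of the sample size and event rates.

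**Which days are exposed.** Days between outpatient contacts are scored retrospectively, so they are not lost. Two kinds remain:
- Days after the last scoring contact. The Day 28 contact may fall on Days 26 to 30. A contact on Day 26 leaves Days 27 and 28 uncovered; one on Day 27 leaves Day 28.
- Days belonging to a missed contact that is not recovered later or from records.

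**Formula applied literally.** Score = number of days d from 1 to 28 with a recorded status of 5 or less; blank days add 0.

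| Patient | Ventilator-free days in fact | SAP score |
|---|---|---|
| Discharged, never ventilated, last scoring contact Day 28, 29 or 30 | 28 | 28 |
| Same, last scoring contact Day 27, later day blank | 28 | 27 |
| Same, last scoring contact Day 26, later days blank | 28 | 26 |
| Same, Day 28 contact missed and unrecovered, not classed as discontinued (last scored Day 20 to 24) | 28 | 20 to 24 |
| Discharged, never ventilated, withdraws after discharge | 28 if course unchanged | 28 by rule |
| Ventilated 2 days, alive, every day scored | 26 | 26 |

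**Size of the tied group.** Every non-event patient should score 28. At the planned rates that is 100 - 26.5 = 73.5% on placebo and 100 - 13.5 = 86.5% on pacritinib.

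**Illustrative simulation.** 100 per arm; events 13.5% versus 26.5%. Event patients start IMV uniformly on Days 2 to 12; half have no further free days and half are ventilated for 5 to 19 days. Non-event patients truly score 28, and 95% of them are discharged by Day 28. A fraction f of discharged non-event patients loses 1 or 2 days. The durations, the 95% and f are assumptions; the documents give none of them. Ranges show repeat runs of the same set-up.

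| f | Wilcoxon power, one-sided 0.10 |
|---|---|
| 0 | 84-85% |
| 5% | 79-81% |
| 10% | 77% |
| 20% | 72-73% |
| 40% | 66-68% |

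The 40% row corresponds to a last contact spread evenly over Days 26 to 30 with nothing filled in: 2 of the 5 days fall before Day 28. About 0.40 x 0.95 x 0.80 = 30% of all patients would then be miscounted, where 0.80 is the mean non-event share, (73.5% + 86.5%)/2. If 90% of those gaps were filled, 4% would remain and power would be about 81%; at 1% to 2% it is about 83%.

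**No true effect.** With gaps equally common in both arms, the two-sided 5% test holds its level: about 5% rejection at 10% in each arm and 5.3% at 40% in each. At 12% versus 10% it rejects 5.2% of the time. It takes an imbalance such as 20% versus 10% to reach 14-15%.

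**The case against.** The strongest reply is that the blanks should not exist. Protocol 7.1.1.1 requires a daily score through Day 28 for everyone, discharged patients included, and 7.1.4.8 says the same of outpatients. On that reading the 2-day window governs the contact and does not excuse the missing scores. Weekly contacts for adverse events and medications run to 30 days after the last dose, about Day 44 after a 14-day course (14 + 30), and records may be reviewed. Days 27 and 28 could be supplied from either source.

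Much of this stands. A reader might infer that days at home are generally lost, or that gaps are unavoidable even under full compliance. The documents support neither reading. What remains is that no text assigns status scoring to contacts after the Day 28 one, and Table 1 schedules none at the 30-day follow-up. Record review is called for only when a patient cannot be reached, which a patient reached on Day 26 does not trigger. If the days stay blank, the SAP has no rule for them.

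The scores of 20 to 24 are also fragile. Protocol 4.2 lists loss to follow-up among the reasons for discontinuation; a discharged, never-ventilated patient so classed receives 28.

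Finally, the trial is not powered on this endpoint, and Protocol 11.3 plans only descriptive statistics for it. That limits the consequence. It does not reconcile the formula with the definition, and the SAP does add a test.

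**Conclusion.** The point holds as a specification gap with a wrong result where it applies: an unscored day in a patient who stays in the study counts as a ventilated day, contrary to the stated definition. SAP section 9 reports no change from the protocol analysis. The 26 versus 28 contrast follows directly from the text, given that Days 27 and 28 stay blank. With every contact made in window the loss is at most 2 days per patient.

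The power cost cannot be fixed from the documents, because the share of unfilled days is unknown. It runs from a few points at 5% to about 17-19 points at 40% (about 85% falling to 66-68%). The 40% case needs both evenly spread contacts and no backfilling, neither of which the documents establish.

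A reader might also infer a bias between arms or an inflated false-positive rate. The documents do not support that. It would need differential missingness, and nothing in a double-blind trial with one contact schedule points to it or gives it a direction.

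**What to change.** In SAP 6.2.1, for patients who did not discontinue early, state for each day from 1 to 28:
- A day with a recorded status of 5 or less is ventilator-free.
- An unscored day is ventilator-free if the nearest scores on both sides are 5 or less, or if it falls after discharge alive with no later record of IMV/ECMO, readmission or death by Day 28.
- All other unscored days, such as an inpatient day next to a status-6 day, and all days from death onward, are not ventilator-free.

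Avoid the shortcut of 28 minus days on IMV/ECMO or dead. It would credit an unscored inpatient day beside a status-6 day, which the rule above does not. Keep the present form-only count as a sensitivity analysis.

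The cost is one paragraph of SAP text and a small derivation change before database lock. No new data are needed: status forms, discharge date and death date are already collected. The downside is small: an unreported reintubation after discharge would be counted as ventilator-free, which the SAP already accepts for discharged early leavers.

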### 6.2.3 Time to Improvement in Clinical Status

The time to improvement in clinical status from baseline will be calculated as:

- Time to Improvement in Clinical Status (days) = Date of improvement in clinical status – date of randomization + 1

The date of improvement in clinical status is defined as the first ordinal scale assessment with a decrease of 2 or more points from the baseline clinical status assessment. For example, for a patient that has a baseline clinical status of 4, the date of improvement would be the first post-baseline clinical status assessment of 2 or 1.

#### **6.2.4    Ordinal Scale of Clinical Status**

The clinical status adapted from [Cao et al.](#) (as described in [Table 3](#)), will be a secondary efficacy outcome variable. The 7-point clinical status score at Day 8, 15, 22 and 28 will be presented by treatment arm using the ITT population.

